### 5.1.3 Subject Exclusion Criteria

The subject must be excluded from participating in the trial if the subject:

1. Has a diagnosis of immunodeficiency or is receiving systemic steroid therapy or any other form of immunosuppressive therapy within 7 days prior to the first dose of trial treatment. Short bursts of steroids of 5-7 days (for COPD exacerbation or other similar indication) are allowed.
2. Has nasopharyngeal or sinonasal carcinoma.
3. Has confirmed metastatic disease. Metastatic disease to neck nodes is considered locally advanced disease and not metastatic and therefore is allowable.
4. Patients who have HPV+ disease of oropharynx. HPV+ disease outside of oropharynx is acceptable.
5. Has a known history of active TB (Bacillus Tuberculosis).
6. Hypersensitivity to Pembrolizumab or any of its excipients.
7. Has a known additional malignancy that was diagnosed within the last five years that is either progressing or requires active treatment. Exceptions include basal cell carcinoma of the skin or squamous cell carcinoma of the skin that has undergone potentially curative therapy or in situ cervical cancer.
8. Has active autoimmune disease that has required systemic treatment in the past 2 years (i.e. with use of disease modifying agents, corticosteroids or immunosuppressive drugs). Replacement therapy (e.g., thyroxine, insulin, or physiologic corticosteroid replacement therapy for adrenal or pituitary insufficiency, etc.) is not considered a form of systemic treatment.
9. Has a history of (non-infectious) pneumonitis that required steroids or has current pneumonitis.
10. Has an active infection requiring systemic therapy.
11. Has a history or current evidence of any condition, therapy, or laboratory abnormality that might confound the results of the trial, interfere with the subject's participation for the full duration of the trial, or is not in the best interest of the subject to participate, in the opinion of the treating investigator.

12. Has known psychiatric or substance abuse disorders that, in the opinion of the investigator, would interfere with cooperation with the requirements of the trial.
13. Is pregnant or breastfeeding, or expecting to conceive or father children within the projected duration of the trial, starting with the pre-screening or screening visit through 120 days after the last dose of trial treatment.
14. Has a known history of Human Immunodeficiency Virus (HIV) (HIV 1/2 antibodies).
15. Has known Hepatitis B (e.g., HBsAg reactive) or known Hepatitis C (e.g., HCV RNA [qualitative] is detected).
16. Has received a live vaccine within 30 days of planned start of study therapy.

*Note: Seasonal influenza vaccines for injection are generally inactivated flu vaccines and are allowed; however intranasal influenza vaccines (e.g., Flu-Mist®) are live attenuated vaccines, and are not allowed.*

## 5.2 Trial Treatments

The treatment to be used in this trial is outlined below in Table 2

Table 2 Trial Treatment

Drug	Dose/ Potency	Dose Frequency	Route of Administration	Regimen/ Treatment Period	Use
Pembrolizumab (Initial infusion)	200 mg	once	IV infusion	Day -21 to -7 (prior to resection)	Experimental
Pembrolizumab	200 mg	Q3W	IV infusion	Day 1 of each 3 week cycle starting 7 days before CRT for 7 doses (including initial dose)	Experimental
Cisplatin	40mg/m2	Weekly	IV infusion	4-8 weeks after resection for 6 doses to begin with radiation	Standard of Care for High Risk only

Radiation	60 Gy	Daily M-F	IMRT	4-8 weeks after resection over 6 weeks	Standard of care
-----------	-------	-----------	------	--	------------------

Treatment will be administered on an outpatient basis. Protocol treatment (pre-surgical Pembrolizumab dose) must begin only after eligibility criteria are confirmed by the UC PI (registration), see study flow for more specific timeframes.

### **5.2.1 Pretreatment Evaluations/Management**

Note: This section lists baseline evaluations needed before the initiation of protocol treatment that **do not** affect eligibility.

#### **5.2.1.1 Required Evaluations/Management**

1. Standard of care dental evaluation with management within 3 months prior to the start of radiation.
2. Assessment of swallowing function/dysphagia using CTCAE, v. 4 criteria prior to the start of radiation.

#### **5.2.1.2 Highly Recommended Evaluations/Management**

1. Assessment by dietitian with recommendations on diet during and after treatment as well as evaluation for prophylactic gastrostomy tube placement (especially if the patient is  $\geq 10\%$  below ideal body weight) within 4 weeks prior to the start of adjuvant treatment.
2. Audiogram evaluation as needed.
3. EKG within 8 weeks prior to the start of treatment.

### **5.2.2 Dose Selection/Modification**

#### **5.2.2.1 Dose Selection**

The rationale for selection of doses to be used in this trial is provided in Section 4.0 – Background and Rationale.

#### **5.2.2.2 Dose Administration**

##### **5.2.2.2.1 Cisplatin Guidelines**

Cisplatin can be given either before or after the radiation therapy fraction that is given on the same day. If radiation is held for more than 2 days (for any reason), Cisplatin may be held as well until radiation resumes. Cisplatin should only continue during radiation and doses should not be made up after the completion of radiation. Patients should receive no more than 6 total doses.

(Note: Cisplatin given within 24 hours of planned administration due to holidays, for example, is acceptable). Weekends count as days.

Patients must be vigorously hydrated before and after Cisplatin administration as per institutional standard regimens. Adequate diuresis is recommended per clinical discretion. A suggested, but not mandatory regimen, would be pre- hydration with 1 liter ½ NS with 1 g MgSO4 and KCL 20mEq over 2 hours and to repeat same after Cisplatin (pre-and post-hydration). Other suggested, but not mandatory, regimens could be 1-1.5 liter NS pre-hydration followed by addition 1-1.5 liter NS post-hydration. Any pre-existing dehydration should be corrected, and additional days of IV fluid can be considered per clinical discretion.

#### **5.2.2.2 Pembrolizumab Guidelines**

Pembrolizumab 200 mg will be administered as a 30 minute IV infusion every 3 weeks. Infuse pembrolizumab (MK-3475) over approximately 30 minutes, with a window of -5 and +10 minutes, through a peripheral line or indwelling catheter. The first dose will be given no more than 3 weeks and no less than 7 days prior to resection. Ideally, the pre-surgery dose of Pembrolizumab will be given between 1-2 weeks before surgery. Post-surgery, Pembrolizumab will be between 4 and 11 weeks and will continue during radiation and 3 months after completion. The first adjuvant Pembrolizumab dose is to begin 1 week prior to radiation.

Pembrolizumab will be administered before Cisplatin on days they are given together. If fluids are administered along with Pembrolizumab, then hydration should include only NS. Radiation may be given before or after infusions. If a Pembrolizumab dose is missed outside the +/-1 day window up to week 7 and +/-3 day window week 10 and beyond per the schedule of events, it should be skipped and not made up.

The Pharmacy Manual contains specific instructions for the preparation of the Pembrolizumab infusion fluid and administration of infusion solution.

#### **5.2.2.3 Radiation Therapy Guidelines**

##### **5.2.2.3.1 Dose Specifications:**

The prescribed radiotherapy dose will be 60-66 Gy in 2-2.2 Gy once-daily fraction size (total of 30-33 fractions). Radiotherapy should begin on a Monday, or Tuesday. The daily dose of 2-2.2Gy Gy will be prescribed such that 95% of the PTV volume receives at least 95% of prescribed dose. The spinal cord dose may not exceed 45 Gy to any volume larger than 0.03 cc.

##### **5.2.2.3.2 Technical Factors**

Treatment Planning/Delivery: Megavoltage energy photon beam irradiation is required. 3D conformal

or IMRT treatment planning may be used, and daily IGRT will be used.

#### **5.2.2.2.3 Localization, Simulation, and Immobilization**

1. Patients must have an immobilization device (e.g., aquaplast mask) made prior to treatment planning CT scan.
2. All patients will undergo CT simulation for treatment planning. The treatment planning CT scan may be completed with or without IV contrast. The treatment planning CT scan must be performed with the immobilization device and in the treatment position. Slice thickness should be 0.3 cm or less.

#### **5.2.2.2.4 Target and Normal Tissue Volume Restrictions**

##### Definition of Target Volumes

CTV60: CTV60 will include the primary tumor bed (based on preoperative imaging, preoperative physical exam/endoscopy, operative findings, pathologic findings) plus the post-operative neck. This volume may include the skin. It is recognized that after surgery, there can be considerable distortion of normal anatomy. If possible, preoperative GTV(s) should be fused onto the postoperative radiation therapy planning CT scan, and appropriate margins added for microscopic spread (1.5-2 cm). CTV60 also will include the ipsilateral pathologically positive hemineck (if both sides of the neck are proven pathologically positive, CTV60 will include both sides). This generally means encompassing nodal levels 2a, 3, and 4. Nodal levels 1, 2b, 5a, and 5b are included in CTV60 in selected circumstances. For questions, contact the Lead Radiology/Oncology Investigator, [name].

CTV56: This will include all other regions felt to be at risk for harboring microscopic cancer that do not meet the criteria for CTV60. For example, this would apply to the contralateral hemineck being irradiated electively for a midline primary cancer.

CTV66 Optional: This may be defined at the discretion of the treating radiation oncologist. This would include a region or regions felt to be at especially high risk for recurrence (e.g., an area of very close margin of resection or nodal extracapsular extension).

Planning Target Volumes (PTVs): In general, the PTV should not go outside of the skin surface; if it does exceed the skin surface, the application of bolus material over this portion of the PTV may be considered to treat skin to full dose.

PTV Expansion The minimum CTV-to- PTV expansion is 3 mm (a larger expansion may be necessary for a target volume subject to significant intra-fraction variability, such as the non-immobilized oral tongue). In general, the CTV-to-PTV expansion should not exceed 10 mm.

##### Definition of Normal Tissues/Organs at Risk (OARs)

Spinal Cord: The cord begins at the cranial-cervical junction (i.e., the top of the C1 vertebral body). Superior to this is brainstem and inferior to this is cord. The inferior border of the spinal cord is at approximately T3-4 (i.e., just below the lowest slice level that has PTV on it). The spinal cord shall be

defined based on the treatment planning CT scan. In addition, however, a Planning Risk Volume (PRV) spinal cord shall be defined. The PRVcord = cord + 5 mm in each dimension.

**Brainstem:** The inferior most portion of the brainstem is at the cranial-cervical junction where it meets the spinal cord. For the purposes of this study, the superior most portion of the brainstem is approximately at the level of the top of the posterior clinoid. The brainstem shall be defined based on the treatment planning CT scan. In addition, however, a Planning Risk Volume (PRV) brainstem shall be defined. The PRVbrainstem = brainstem + 3 mm in each dimension.

**Lips and Oral Cavity:** These should be contoured as 2 separate structures as the goal is to keep the lip dose much lower than the oral cavity dose. The definition of lips is self-explanatory. The oral cavity will be defined as a composite structure consisting of the anterior 1/2 to 2/3 of the oral tongue/floor of mouth, buccal mucosa, and palate.

**Parotid Glands:** Parotid glands will be defined based on the treatment planning CT scan.

**OARpharynx:** This will be defined as the “uninvolved” posterior pharyngeal wall plus adjacent constrictor muscles. This extends from the superior constrictor region (the inferior pterygoid plates level) to the cricopharyngeal inlet (posterior cricoid cartilage level). This should not overlap the PTVs.

**Cervical Esophagus:** This will be defined as a tubular structure that starts at the bottom of OARpharynx and extends to the thoracic inlet.

**Glottic/Supraglottic Larynx (GSL):** Obviously, for patients who have had a total laryngectomy, this structure is not applicable. This will be defined as a “triangular prism shaped” volume that begins just inferior to the hyoid bone and extends to the cricoid cartilage inferiorly and extends from the anterior commissure to include the arytenoids. This includes the infrahyoid but not suprathyoid epiglottis.

**Mandible:** This includes the entire boney structure of the mandible from TMJ through the symphysis. It is recognized that for oral cavity cancers, this may overlap with CTVs and PTVs.

**Unspecified Tissue Outside the Targets:** This will be defined as tissue located between the skull base and thoracic inlet that is not included in either the target volumes or the normal tissues described above.

#### **5.2.2.2.5 Treatment Planning and Delivery Dose Prescription to PTVs**

As described in Section 5.2.2.2.1, prescribed radiotherapy dose will be 60-66 Gy in 2-2.2 Gy once daily fraction size. For inverse planning IMRT, the goal is for 95% of the PTV60 to receive 95% of 2 Gy with a minimum dose (cold spot) of no less than 56 Gy. It is recognized that portions of the PTV60 close to/within the skin may receive significantly less than 56 Gy. Bolus should be considered for these cutaneous areas deemed to be at risk for microscopic disease.

For IMRT prioritization, PTV60 will be the highest priority target structure. PTV66 and PTV56, if applicable, will be ranked in the IMRT planning as lower priority than PTV60 although higher priority than normal structures other than spinal cord and brain stem.

#### 5.2.2.2.6 Dose Constraints to Normal Structures

Spinal Cord: The PRVcord (as defined in Section 6.4.2.1) should not exceed 45 Gy to any volume in excess of 0.03 cc (approximately 3 mm x 3 mm x 3 mm). The spinal cord PRV should not exceed 50 Gy to any volume in excess of 0.01 cc. In treatment planning, the spinal cord PRV should be given the highest priority.

Brainstem: The PRVbrainstem (as defined in Section 6.4.2.2) should not exceed 50 Gy to any volume in excess of 0.03 cc (approximately 3 mm x 3 mm x 3 mm). In treatment planning, the PRVbrainstem should be given less priority than the PRVcord but more priority than the other critical structures listed below.

Lips: Reduce the dose as much as possible unless lips involved with primary tumor. The mean dose should be < 20 Gy. The maximum dose will be < 35 Gy.

Oral Cavity: (uninvolved) Reduce the dose as much as possible. The mean dose should be < 30 Gy.

Parotid Glands: In most cases, it will be easier to spare one parotid than the other. The treatment planning goal will be for this individual parotid gland to receive a mean dose of < 26 Gy. Additional planning goals may include: 1) At least 50% of one parotid will receive < 30 Gy; and/or 2) At least 20 cc of parotid tissue (from the combination of both glands) will receive < 20 Gy.

OARpharynx: Reduce the dose as much as possible. Some recommended (but not mandatory) treatment goals include: 1) No more than 33% of the OARpharynx exceeds 50 Gy; 2) Mean dose < 45 Gy; 3) No more than 15% of the OARpharynx exceeds 60 Gy.

Cervical Esophagus: Reduce the dose as much as possible. For oral or oropharyngeal cancer, some recommended (but not mandatory) treatment goals include: 1) No more than 33% of the esophagus exceeds 45 Gy; 2) Mean dose < 35 Gy; 3) No more than 15% of the esophagus exceeds 54 Gy. For larynx cancer, higher doses are expected and permitted. Some recommended doses (but not mandatory) treatment goals include: 1) No more than 33% of the esophagus exceeds 50 Gy; 2) Mean dose < 45 Gy; 3) No more than 15% of the esophagus exceeds 60 Gy.

Glottic and Supraglottic larynx (GSL): Reduce the dose as much as possible. Goal should be mean < 35Gy.

Mandible: Reduce the dose as much as possible, hot spots within the mandible should be avoided. It is recommended that maximum dose within the mandible be < 66 Gy. For tumors that were not clinically or pathologically involving the mandible, the CTV should be contoured off the mandible.

Unspecified Tissue Outside the Targets: For the typical case in which there is no CTV66, no more than 5% of unspecified tissue can receive greater than 58 Gy and no more than 1% or 1cc of unspecified tissue can receive 64 Gy or more. When a boost is used to increase the dose to high risk regions to as much as 66 Gy, these numbers can be increased. In this case, no more than 5% of the unspecified dose should exceed the level of the boost dose, and no more than 1% or 1 cc should exceed the boost dose value plus 10%.

### **5.2.2.2.7 Compliance Criteria**

Treatment breaks for radiation must be clearly indicated in the treatment record along with the reason(s) for the treatment break(s). Treatment breaks, if necessary, ideally should not exceed five treatment days at a time and ten treatment days total. Treatment breaks should be allowed only for resolution of severe acute toxicity and/or for intercurrent illness and not for social or logistical reasons.

### **5.2.2.2.8 Radiation Therapy Adverse Events**

The descriptions and grading scales found in the revised NCI Common Terminology Criteria for Adverse Events (CTCAE), version 4.0 will be utilized for grading all adverse events. Placement of a feeding tube should be recorded as adverse event “use of a feeding tube during and after treatment” (e.g., greater than or less than 50% of nutrition by tube). Other common radiation adverse events include: fatigue, weight loss, regional alopecia, xerostomia, hoarseness, transient ear discomfort, and skin erythema and desquamation within the treatment fields. Less common long-term treatment adverse events include: hypothyroidism, loss of hearing, chronic swallowing dysfunction requiring permanent feeding tube, and skin/soft tissue fibrosis. Much less common radiation adverse events include: mandibular osteoradionecrosis, and cervical myelopathy (< 1% with restriction of spinal cord dose to max dose of 45 Gy).

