Nausea and Vomiting: Maximum supportive therapy will be given, and Cisplatin will be continued at full dose for  $\leq$  grade 2 nausea and vomiting. For grade 3 nausea and vomiting refractory to supportive therapy, Cisplatin will be held until recovery to < grade 2. No dose reductions will be made.

Mucositis: Significant mucositis (grade 3-4, CTCAE, v. 4) is expected from radiation and Cisplatin and should not be a reason for a treatment break, unless it significantly interferes with fluid intake or nutrition. Aggressive supportive care is encouraged as well as consideration of a PEG tube if not already

done.

Ototoxicity: For clinical hearing loss not requiring a hearing aid, reduce Cisplatin by 2 dose levels (23mg/m^2). For hearing loss requiring a hearing aid, discontinue Cisplatin. For grade 2-3 tinnitus (CTCAE, v. 4) at the time of retreatment, hold Cisplatin until improvement to grade 1 or less and then reduce the following doses of Cisplatin by 2 dose levels. If tinnitus does not improve to grade 1 or less by the last day of radiation therapy, discontinue Cisplatin. An audiogram is recommended when there is any report of significant change in hearing and/or an increase in tinnitus.

Other Toxicities: For any other grade 3-4 adverse events, hold Cisplatin until toxicities have recovered to grade 1 or less. Dose may be reduced by 1 or 2 dose levels for next treatment if felt necessary by discretion of investigator.

If any doses of Cisplatin are skipped due to hematologic, neurologic, renal, or other adverse events, these doses will NOT be made up at end of treatment. Cisplatin will continue only during time of radiation treatment. If a weight change of  $\geq 10\%$  occurs, the following Cisplatin doses should be adjusted.

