### **7.2 Assessing and Recording Adverse Events**

An adverse event is defined as any untoward medical occurrence in a patient or clinical investigation subject administered a pharmaceutical product and which does not necessarily have to have a causal relationship with this treatment. An adverse event can therefore be any unfavorable and unintended sign (including an abnormal laboratory finding, for example), symptom, or disease temporally associated with the use of a medicinal product or protocol-specified procedure, whether or not considered related to the medicinal product or protocol-specified procedure. Any worsening (i.e., any clinically significant adverse change in frequency and/or intensity) of a preexisting condition that is temporally associated with the use of Merck's product, is also an adverse event.

Changes resulting from normal growth and development that do not vary significantly in frequency or severity from expected levels are not to be considered adverse events. Examples of this may include, but are not limited to, teething, typical crying in infants and children and onset of menses or menopause occurring at a physiologically appropriate time.

Merck product includes any pharmaceutical product, biological product, device, diagnostic agent or protocol-specified procedure, whether investigational (including placebo or active comparator medication) or marketed, manufactured by, licensed by, provided by or distributed by Merck for human use.

Adverse events may occur during the course of the use of Merck product in clinical trials or within the follow-up period specified by the protocol, or prescribed in clinical practice, from overdose (whether accidental or intentional), from abuse and from withdrawal.

Adverse events may also occur in screened subjects during any pre-allocation baseline period as a result of a protocol-specified intervention, including washout or discontinuation of usual therapy, diet, placebo treatment or a procedure.

Progression of the cancer under study is not considered an adverse event unless it is considered to be drug related by the investigator.

All adverse events will be recorded from the time the consent form is signed through 30 days following cessation of treatment and at each examination on the Adverse Event case report forms/worksheets. The reporting timeframe for adverse events meeting any serious criteria is described in section 7.2.3.1.

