## **8.0 STATISTICAL ANALYSIS PLAN**

### **8.1 Statistical Analysis Plan Summary**

#### **8.1.1 Safety Analysis**

The All-Patients-as-Treated (APaT) population will be employed for safety analyses. The safety endpoints are all adverse events graded from 1 to 5. Fisher's exact test will be used to compare the proportion of adverse events among patients treated by Pembrolizumab + radiotherapy in this study with historical patients treated by radiotherapy only and compare patients treated by Pembrolizumab + radiotherapy + Cisplatin in this study with historical patients treated by radiotherapy + Cisplatin. Both the adverse events by grade as well as severe adverse event (SAE; yes/no) will be analyzed. RTOG 9501 data will be used for historical controls using targeted rates of 50% for CRT and 39% for RT. We expect that the addition of Pembrolizumab will not add undue toxicity over standard treatment and therefore, will give insight to the development of future trials.

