## **8.2.4 Statistical Methods**

### **8.2.4.1 Safety Analysis**

Descriptive statistics will be provided for safety endpoints. Exact test will be used to compare patients treated by Pembrolizumab + radiotherapy in this study with historical patients treated by radiotherapy only (targeted rate of grade 3 and 4 adverse effects is 39%) and compare patients treated by Pembrolizumab + radiotherapy + Cisplatin in this study with historical patients treated by radiotherapy + Cisplatin (targeted rate of grade 3 and 4 adverse effects is 50%).

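### Feeding tube placement is recorded as an adverse event without separating prophylactic from reactive tubes, so a preventive procedure can enter the safety endpoint compared with RTOG 9501

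*Combined protocol and SAP*

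**What the plan says.** **Recording rule.** Section 5.2.2.2.8 states "Placement of a feeding tube should be recorded as adverse event". The event label that follows is worded as tube use, with a descriptor for whether more or less than half of nutrition goes through the tube. The section makes no exception for a preventive tube, asks for no reason, and assigns no grade beyond the general reference to CTCAE version 4.0.

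**Prophylactic tubes.** Section 5.2.1.2 lists, among highly recommended steps in the 4 weeks before adjuvant treatment, a dietitian assessment that includes "evaluation for prophylactic gastrostomy tube placement (especially if the patient is" at least 10% under ideal body weight).

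**Collection window.** Section 7.2 states "All adverse events will be recorded from the time the consent form is signed through 30 days following cessation of treatment". A tube placed after consent and before radiation falls inside this window.

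**Analysis.** Section 8.2.1 makes adverse events of all grades the safety endpoint. Section 8.1.1 adds "Both the adverse events by grade as well as severe adverse event (SAE; yes/no) will be analyzed" and "RTOG 9501 data will be used for historical controls using targeted rates of 50% for CRT and 39% for RT". Section 8.2.4.1 ties those figures to grade 3 and 4 events: "targeted rate of grade 3 and 4 adverse effects is 50" percent for CRT and "targeted rate of grade 3 and 4 adverse effects is 39" percent for RT. Section 8.2.3.1 limits the historical comparison to patients who continue treatment after resection. None of these sections filters by attribution or sets preventive procedures aside.

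**The concern.** The frequency and severity of side effects is the first primary objective (section 3.1). A tube placed as a precaution before any radiation or cisplatin is not a side effect, yet the recording rule turns on placement and gives no means of telling it from a tube placed because the patient could no longer swallow. Such tubes could add to the all-grade tables. If graded 3 or higher, they could also add to a rate that is tested against fixed historical figures. The documents do not say whether those figures include tubes, so the two sides may not be counted alike.

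**Working it through.** **Is there a figure to reproduce?** The plan states no power, alpha, direction or decision rule for the safety comparison. The only stated power is for 1-year DFS (section 8.1.3: N=40, one-sample exact test, one-sided 0.025). Those figures reproduce:
- 65% against 86% needs at least 33/40 and has power 0.811.
- 69% against 88% needs at least 34/40 and has power 0.802.

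The same test form is borrowed below for safety, as an assumption.

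**Inputs from the plan.** N=40 per stratum (section 8.1.3); p0 = 0.50 for CRT and 0.39 for RT (section 8.2.4.1).

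**Inputs assumed.**
- The test is one-sided, upper tail, at 0.025, with the historical rate taken as fixed.
- The true grade 3-4 rate equals p0.
- A fraction q of patients has a prophylactic tube that is graded 3, independently of any other grade 3-4 event.

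**Step 1: critical values.** The smallest r with P(X ≥ r | 40, p0) ≤ 0.025 is:
- CRT: r = 27 (actual alpha 0.0192)
- RT: r = 23 (actual alpha 0.0136)

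**Step 2: counted rate.** A patient counts if there is a real grade 3-4 event or, failing that, a tube: p = p0 + (1 − p0)q.
- CRT: 0.50 + 0.50 × 0.10 = 0.55; 0.50 + 0.50 × 0.20 = 0.60
- RT: 0.39 + 0.61 × 0.10 = 0.451; 0.39 + 0.61 × 0.20 = 0.512

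**Step 3: probability of a false excess-toxicity signal,** P(X ≥ r | 40, p):

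| q | CRT counted rate | CRT false signal | RT counted rate | RT false signal |
|---|---|---|---|---|
| 0 | 50% | 1.9% | 39% | 1.4% |
| 10% | 55% | 7.5% | 45.1% | 7.9% |
| 20% | 60% | 21.1% | 51.2% | 26.2% |

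**Sensitivity to the assumptions.**
- At one-sided 0.05 the values for CRT and RT are 4.0% and 2.9% at q = 0, 13.3% and 13.6% at q = 10%, and 31.7% and 37.4% at q = 20%.
- If 20% of patients have such tubes but half are graded below 3, the effective q is 0.20 × 0.5 = 10%, and that row applies.
- If none is graded 3 or higher, q = 0 for this test and only the all-grade counts change.
- If tubes go mainly to patients who have grade 3-4 events anyway, the excess is smaller than shown.

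**The case against.** **The event is tube use, not placement.** The full sentence in section 5.2.2.2.8 names use and share of nutrition, and section 7.2 defines an adverse event as something untoward. A site could reasonably leave out an unused preventive tube. This stands as an ambiguity. It does not remove the problem, because the instruction itself is triggered by placement and sites could read it either way.

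**Nothing makes a preventive tube grade 3.** This stands. Table 6 in section 7.2.4 keeps grade 3 for severe or medically significant events, and no section grades the tube. The route to the grade 3-4 test is therefore conditional.

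**The mucositis guidance is not about prophylaxis.** This stands. Section 5.2.2.4.2 says "Aggressive supportive care is encouraged as well as consideration of a PEG tube if not already" in place, but it does so when discussing grade 3-4 mucositis. A patient with that toxicity already counts, so the tube adds nothing to a patient-level rate. Section 5.2.1.2, for its part, recommends evaluation, not placement.

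**The direction of bias is unknown.** This also stands. If the RTOG 9501 rates include tubes, removing prophylactic tubes from the trial side alone would understate toxicity.

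**The data partly exist.** Start dates and relationship to pembrolizumab are recorded (Table 6), and section 5.2.1.1 requires a pre-radiation CTCAE swallowing assessment. This makes the fix cheap, but the analysis sections do not call for the separation.

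**Conclusion.** The recording rule can count a preventive procedure in a primary safety endpoint. The effect on the all-grade endpoint follows from the text as written. The effect on the comparison with 50% and 39% arises only if such tubes are graded 3 or higher. The rise from 1-2% to about 8-26% illustrates sensitivity under an assumed tube share, grade, independence and alpha. It does not estimate what will happen in this trial.

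Stronger conclusions are tempting and are not supported:
- A reader might infer that the trial is likely to report excess toxicity that does not exist, since the same calculation gives 44.1% (CRT) and 55.6% (RT) at q = 30%. No document gives a tube rate or grade that would support such a share, or says how RTOG 9501 counted tubes.
- A reader might infer that the toxicity rate would measure local tube practice and not pembrolizumab. One ungraded item among all adverse events does not show that, and the documents do not describe tube practice at any site.
- A reader might infer that the lead-in stopping rule is affected. Section 5.2.2.3.1 requires an event attributed to pembrolizumab that also delays standard treatment, so the rule is largely untouched.

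**What to change.** **In section 5.2.2.2.8:** record for each tube the placement date, the reason (prophylactic or reactive) and whether it is used for nutrition. Grade the underlying toxicity, not the procedure; for example, grade dysphagia relative to the pre-radiation CTCAE assessment in section 5.2.1.1.

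**In section 8.2.4.1:** report the grade 3-4 comparison with and without prophylactic tubes. Make the main version the one that matches how the RTOG 9501 rates were counted, if that can be established. List prophylactic tubes separately.

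**Cost:** one more CRF field, since the start date is already collected for adverse events, and one sensitivity analysis. The change affects recording and analysis only; decisions on placing tubes stay as they are.
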